10.3.2.4 Supply, Packaging and Storage

The Apne-Scan DC1 kit will be provided to the study participant by the sleep centre. It will contain all the items outlined in 10.3.2.1 above. Apnea-Tech do not believe that there are any requirements for secure packaging or long-term storage. The shelf life of the batteries is the current limitation on use, and this is over 24 months.

10.3.2.5 Administration

The study team will maintain a Device Register which will identify to which participant each device was issued, so that they can be tracked.

10.3.2.6 Disposal of items

Once returned to Apnea-Tech, the Apne-Scan is dismantled, with the battery and electrical components recycled appropriately (under WEEE). The mask, sensor and Apne-Scan enclosure will be recycled according to their specific requirements.

10.3.3 Assessment questionnaire

After using the Apne-Scan DC1, each study participant will complete a short questionnaire which is on the back of the study participant's baseline details completed by the study team after informed consent (age, sex, ethnicity, weight, neck circumference, smoking history, Epworth score and baseline saturations at rest). The questionnaire, which is not a validated questionnaire, enables the participant to record their experience in using the Apne-Scan DC1.

10.4 Discontinuation/Withdrawal of Participants from the study

Participants will be free to withdraw from the study at any time without any consequences or compromise to their standard clinical care. Participants will consent at the start of the study to allow

for their anonymised study data (baseline information, questionnaire data and Apne-Scan data) to be retained and analysed by the study team in the event that they withdraw from the study.

10.5 Definition of End of Study

The end of study is the date at which the final participant completes the study and returns their device to Apnea-Tech. The minimum evidence for successful completion of the study is at least 15 participants capturing between them sixty hours of breathing data.

11. SAFETY

11.1 Safety Reporting Definitions

Adverse Event Categorisation

Adverse Events	Non-Device-Related	Device- or Investigational Procedure-Related	
Non-Serious	Adverse Event (AE)	Adverse Device Effect (ADE)	
Serious	Serious Adverse Event (SAE)	Serious Adverse Device Effect (SADE)	
		Anticipated	Unanticipated
		Anticipated serious adverse device effect (ASADE)	Unanticipated serious adverse device effect (USADE)

11.1.1 Adverse Event (AE)

An untoward medical occurrence, unintended disease or injury, or untoward clinical signs (including abnormal laboratory findings) in participants, users or other persons, whether or not related to the investigational medical device and whether anticipated or unanticipated.

An AE can, therefore, be any unfavourable or unintended sign, symptom or disease temporarily associated with the use of the device, whether or not this has a causal relationship with the device under investigation.

11.1.2 Adverse Device Effect (ADE)

An adverse event related to the use of an investigational medical device.

Note 1: This definition includes adverse events resulting from insufficient or inadequate instructions for use, deployment, implantation, installation, or operation, or any malfunction of the investigational medical device.

Note 2: This definition includes any event resulting from use error or from intentional misuse of the investigational medical device.

ADEs are all untoward and unintended medical occurrences in response to a medical device. All cases judged by either a medically qualified professional or the sponsor as having a reasonable suspected causal relationship to the device qualify as a device effect. This also includes any event resulting from insufficiencies or inadequacies in the instruction for use or deployment of the device and includes an event that is a result of a user error.

11.1.3 Serious Adverse Events (SAE)

An adverse event that led to any of the following:

- Death
- Serious deterioration in the health of the participant, users, or other persons as defined by one or more of the following:
 - A life-threatening illness or injury
 - A permanent impairment of a body structure or a body function including chronic diseases
 - In-patient or prolonged hospitalisation
 - Medical or surgical intervention to prevent life-threatening illness or injury, or permanent impairment to a body structure or a body function
 - Foetal distress, foetal death, a congenital abnormality, or birth defect including physical or mental impairment

Note: Planned hospitalisation for a pre-existing condition, or a procedure required by the protocol, without serious deterioration in health, is not considered a serious adverse event.

The term 'life-threatening' in the definition of 'serious' refers to an event in which the participant was at risk of death at the time of the event; it does not refer to an event which hypothetically might have caused death if it were more severe.

Other events that may not result in death, are not life-threatening or do not require hospitalisation, may be considered a serious adverse event when, based upon appropriate medical judgement, the event may jeopardise the participant and may require medical or surgical intervention to prevent one of the outcomes listed above.

11.1.4 Anticipated Serious Adverse Device Effects (ASADE)

A serious adverse device effect which by its nature, incidence, severity or outcome has been identified in the risk assessment.

11.1.5 Unanticipated Serious Adverse Device Effects (USADE)

A serious adverse device effect which by its nature, incidence, severity or outcome has not been identified in the current risk assessment.

11.1.6 Serious Adverse Device Effects (SADE)

An adverse device effect that has resulted in any of the consequences characteristic of a serious adverse event.

A SADE does not necessarily have to have a causal relationship with the device under investigation. However, a SADE is defined as any untoward medical occurrence seen in a participant that can be attributed wholly or partly to the device which resulted in any of the characteristics or led to the characteristics of a SAE. A SADE is also an event that may have led to these consequences if proper action had not been taken or intervention had not been made or if circumstances had been less opportune. A SADE will be documented on a SAE form.

11.1.7 Serious Health Threat (SHT)

A signal from any adverse event or device deficiency that indicates an imminent risk of death or a serious deterioration in the health in participants, users or other persons, and that requires prompt remedial action for other subjects, users or other persons.

Note: This would include events that are of significant and unexpected nature such that they become alarming as a potential serious health hazard or possibility of multiple deaths occurring at short intervals.

11.2 Recording & Reporting of Adverse Events

11.2.1 Sponsor Responsibilities

The Sponsor is responsible for the following activities:

- In collaboration with the Device Manufacturer, perform on-going safety evaluation of the trial device and report any findings that may affect the health of participants to the Device Manufacturer.
- Promptly notify all Investigators, REC and MHRA (if required), of any findings that may affect the health of participants.
- Keep detailed written reports of all AEs reported by PI(s) and review the PI's evaluation of the AE's seriousness, causality and expectedness.
- Report all relevant safety information and SAEs to the CI, REC and MHRA (if required) within the relevant timelines given in the protocol.
- Break treatment codes before submitting expedited reports to MHRA and REC for specific participants, even if the Investigator has not broken the code.
- Submit the annual safety report to REC.
- Submit summary reports to the MHRA (if required).

11.2.2 Chief Investigator Responsibilities

The Chief Investigator has overall responsibility for the conduct of the study and will provide the Sponsor with details of all AEs identified in the protocol as critical to the evaluation of safety.

11.2.3 Principal Investigator Responsibilities

The Principal Investigator will be a different person to the Chief Investigator and will:

- Inform the Sponsor (UHNM) of all adverse events that occur at their site.
- Inform the Sponsor within 24 hours of being notified that the event has occurred.
- Assess the AE severity, causality and expectedness and update the Sponsor on the results of their assessment within 48 hours of being notified that the event has occurred.
- Supply the Sponsor, and the MHRA and REC (where necessary), with any supplementary information they request.

11.3 Recording & Reporting of Adverse Events

Participants will be asked to report any AEs to the clinical study team. AEs will be assessed by the CI for causality, intensity, seriousness and expectedness. Only AEs that have a reasonable possibility of being attributable to the device and any other AE considered to be of clinical significance by the CI as causing harm to the participant will be recorded and reported to the Sponsor. Any SAEs that do occur and are considered by the CI to be related to the device will be expedited to the Sponsor and the REC within 7 days. Lists of the AEs will be provided by the Sponsor when requested.

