7.2 Outcome Measures

7.2.1 Research outcomes:

Primary Outcome

The primary outcome of interest is the data capture of the changing pressures in the user's breathing, whilst asleep, as recorded by the Apne-Scan DC1 device.

Note: The minimum evidence for successful completion of the study is 60 hours of breathing data captured by a minimum of 15 participants.

Secondary Outcomes

- An overall comparison of the OSA screening output from Apne-Scan DC1 with that from standard sleep apnoea test devices (ResMed NOX T3 and Phillips Alice Night One).
- A comparison stratified by the severity of the OSA indicated by standard sleep apnoea test devices.
- A comparison stratified by the severity of the hypopnoea indicated by standard sleep apnoea test devices.
- A possible first-generation algorithm, based on the Apne-Scan data, to predict the user's SPO2 level.

7.2.2 Safety Outcomes:

- Any adverse events (AEs) reported while performing the study procedures.
- Any adverse device effects (ADEs).

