11.3.1 Assessment of Adverse Events

Initial assessment of AEs must be made by the Principal Investigator using the relevant safety reporting form. The outcome of this assessment should be forwarded to the Sponsor for Sponsor review **within 48 hours** of the AE being detected by the research team. If the AE is determined to be serious, it must then be reviewed by the CI.

Each AE must be assessed for seriousness, causality and expectedness. Where the PI and Sponsor's reviews do not concur, the AE must be followed up as the more serious event.

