11.3.2.1 Assessment of Expectedness

The assessor must consult the current version of the protocol to determine whether an event is expected or unexpected. Events that are anticipated (or 'expected') are listed below. An unanticipated (or unexpected) effect is anything not listed in the protocol.

Anticipated (Expected) Events:

Code	Event	Frequency
01	Breathlessness/intolerance to mask	High
02	Apnoeas/cessation of breathing	High
03	Hypopneas/shallow breathing	High
04	Snoring	High
05	Restlessness/poor sleep	High
06	Snoring	High
07	Irregular breathing	High
08	Any other event directly related to diagnosis of suspected sleep apnoea	High
09	Any other event directly related to the participant's existing medical conditions	High

If the event is classified as an anticipated effect (i.e. expected), which by its nature, incidence severity or outcome has been previously identified in the Protocol, then the event does not require reporting to the Regulatory Agencies (MHRA and REC) but must be recorded in the medical records and the relevant safety reporting form. The sponsor must be informed of this event **within 48 hours** of becoming aware of the event. This document must be retained with the CRF.

Where an event could be related to the medical device and is unanticipated, in relation to the protocol (i.e. a USADE or unexpected SAE), the PI must report this event to the Sponsor **within 24 hours** of becoming aware of the event. The Sponsor will report this event to both the Manufacturer and to the Regulatory Agencies within the required timelines.

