11.4.3 Reporting Serious Adverse Events

Reporting to Sponsor:

If the PI determines that the AE is serious, the relevant safety reporting form must be used to report all SAEs/SADEs/USADEs/ASADEs to the Sponsor. This form and any documents provided to the Sponsor in support of the SAE/SADE/USADE must be depersonalised (labelled with trial ID number) and must NOT contain any patient identifiable data.

The PI/research team at the site where the AE occurred must provide any additional information as required to complete the report. The PI/research team at site must actively following-up the affected participant(s) until either:

- The SAE/SADE/USADE resolves, or
- Until 30 days after the discontinuation of use of the medical device

Review and sign-off of SAEs:

The CI is responsible for the review and sign-off of all serious adverse events/effects. In the event that the CI is unable to sign the report immediately, the research team/site should not delay sending the report to the Sponsor. However, a CI signed copy must be forwarded to the Sponsor as soon as possible (and within 48 hours of the initial reporting).

Should the CI be unavailable, serious adverse events/effects can be signed off by [name].

Reporting to the MHRA:

Device related events involving a CE/UKCA marked device being used within its intended purpose/proof of concept studies in a post market surveillance study must be reported to the MHRA Adverse Incident Centre <https://aic.mhra.gov.uk/>. Reporting to the MHRA of such occurrences is undertaken by the Sponsor. Individual guidance on the reporting requirements for certain types of devices can be found on the MHRA website

<https://www.gov.uk/government/collections/medical-devices-guidance-for-manufacturers-on-vigilance>

Reporting to REC:

The following SAEs/SADEs are considered reportable to the REC that gave the favourable ethical opinion:

- Those related to the administration of the medical device or any of the research procedures.
- USADEs - i.e. unanticipated events not listed in the Protocol as an anticipated occurrence.

Reports to REC should be submitted, by the Sponsor, within 15 days of the CI becoming aware of the event using the Non-CTIMP Safety Report Form to the REC published on the HRA website <http://www.hra.nhs.uk/>.

The CI is also required to include a report of the safety of participants in the annual progress report to the REC.

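### Section 11.3 would record only a CI-filtered subset of adverse events although the safety outcome is any reported AE; separately, section 11 conflicts on REC exemption, clocks and assessor

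*Combined protocol and SAP*

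**What the plan says.** **What counts and what is recorded.** Section 7.2.2 names as its first safety outcome "Any adverse events (AEs) reported while performing the study procedures". Section 11.1.1 defines an AE without regard to device relationship or to whether it was expected. Section 11.3 has participants asked to tell the clinical team of any AE and has the CI assess what they report. It then narrows what is kept: "Only AEs that have a reasonable possibility of being attributable to the device and any other AE considered to be of clinical significance by the" Chief Investigator, on grounds of harm to the participant, go into the record and on to the Sponsor.

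Three other sections carry no such filter. Under 11.2.3 the Principal Investigator (PI) must "Inform the Sponsor (UHNM) of all adverse events that occur at their site". Under 11.4.1 the PI's assessment of every AE goes to the Sponsor within 48 hours. Under 11.4.2 every AE goes to the DMC and to the next TSC.

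**Who assesses and who is told.** Section 11.3 gives the assessment to the CI. Section 11.3.1 says "Initial assessment of AEs must be made by the Principal Investigator", and 11.2.3 requires the PI and CI to be different people. For serious events that the CI considers device-related, 11.3 says they "will be expedited to the Sponsor and the REC within 7 days". Section 11.3.2.1 says of an anticipated event "then the event does not require reporting to the Regulatory Agencies (MHRA and REC"). Section 11.4.3 lists as REC-reportable serious events "Those related to the administration of the medical device or any of the research procedures", has a second bullet for unanticipated serious device effects, and adds "Reports to REC should be submitted, by the Sponsor, within 15 days of the CI becoming aware of the event".

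**The concern.** A safety outcome is only as complete as the rule that decides what is written down. If causality and clinical significance are judged first and recording depends on the answer, the recorded set reflects one person's judgement, and nobody can later check how many events were set aside or why. A table of AEs built from it would carry the label of 7.2.2 but contain something narrower.

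This matters for a device which, according to section 5.2, has so far been worn overnight only by people involved in its development, in prototype and development versions. Section 9 says that the results will inform a larger study, and the AE profile is part of what that study would draw on.

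The second group of conflicts is of another kind. It concerns whether, by whom and how fast a serious event is passed on. Two people following different sections could handle the same event differently and both be able to cite the protocol.

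**Working it through.** No arithmetic applies: the plan gives no AE rate, and the only figures are reporting times. The check is to take three types of event through each section.

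| Section | A: non-serious, judged unrelated and not clinically significant | B: serious, device-related, anticipated | C: serious, device-related, unanticipated |
|---|---|---|---|
| 7.2.2 with 11.1.1 | Part of the outcome once reported | Part of the outcome | Part of the outcome |
| 11.2.3 | Sponsor told in 24 hours | Sponsor told in 24 hours | Sponsor told in 24 hours |
| 11.3 | Not recorded, not sent to Sponsor | Sponsor and REC in 7 days | Sponsor and REC in 7 days |
| 11.3.2.1 | If on the anticipated list: recorded, Sponsor told in 48 hours | Recorded, Sponsor told in 48 hours; no MHRA or REC report required | Sponsor told in 24 hours; regulatory reports follow |
| 11.4.1 | Assessment to Sponsor in 48 hours | Same | Same |
| 11.4.2 | DMC and TSC | DMC and TSC | DMC and TSC |
| 11.4.3 | Not applicable | REC in 15 days, reading its bullets separately | REC in 15 days |

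**Column A: the outcome.** Such an event belongs to the outcome and must reach the Sponsor under 11.2.3 and 11.4.1, yet 11.3 leaves it unrecorded. One could try to reconcile these by taking the word for reporting in 7.2.2 to mean reported to the Sponsor after the filter. Section 11.3 itself counts against that, since it uses the same word for the participant telling the clinical team, which is the step before the filter. Nor does another part of the plan supply the missing data: the schedule of events in 10.3.1 has no AE row, the data list in 12.2 has no AE item, and section 13 names no AE summary.

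**Column B: the REC route.** Section 11.3 sends the event to the REC and makes no exception for anticipated events. Section 11.3.2.1 exempts anticipated events and does not expressly exclude serious ones. The anticipated list includes mask intolerance, cessation of breathing and two open categories (codes 08 and 09), so the overlap is not empty.

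**Columns B and C: the REC clock.** It is 7 days in 11.3, with no starting point stated, and 15 days from CI awareness in 11.4.3. The difference is 15 − 7 = 8 days. If both are counted from CI awareness (an assumption for 11.3), a report on day 10 is in time under one section and late under the other.

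**The Sponsor clock.** Not every difference here is a conflict. Section 11.2.3 separates notification (24 hours) from the completed assessment (48 hours), so the 48 hours in 11.3.1 and 11.4.1 fit it. The conflicts are the 48 hours for first informing the Sponsor of anticipated events in 11.3.2.1 and the 7 days for related serious events in 11.3, each against 24 hours for all events in 11.2.3.

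**The case against.** The best defence is that 11.3 is one sentence against several. Sections 11.2.3, 11.3.1, 11.4.1 and 11.4.2 all point to complete capture, 11.2.1 has the Sponsor keep written reports of all AEs that the PI passes on, and 11.3.2.1 requires even anticipated events to be recorded on the safety form. The filter also is not causality alone, because the CI may keep any event thought clinically significant. All of this stands. A reader might infer that safety cannot be reported at all, or that nothing is written down before the filter. The documents do not support either: the loss occurs only if 11.3 prevails.

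On the REC, 11.3.2.1 ties the exemption to events whose nature, incidence, severity or outcome the protocol has already identified, and its list describes no serious form. It can therefore be read as excluding serious events. Against this, the criteria are alternatives, so nature alone may suffice, and 11.1.4 expressly recognises serious device effects that are anticipated. The two bullets in 11.4.3 may also have been meant jointly (related and unanticipated), which would fit 11.3.2.1. The conflict would then be between 11.3 and 11.3.2.1 only, but it would remain.

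A reader might also infer that a related serious event could stay hidden from the REC for good. That goes too far. Sections 11.2.1 and 11.4.3 require annual safety reporting to the REC, unanticipated serious device effects are REC-reportable throughout, and the exemption removes a requirement without forbidding a report. Only event-level reporting of anticipated events is in doubt.

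Finally, a second assessor is not a fault in itself. Initial review by the PI, CI review of serious events and Sponsor review form a deliberate sequence. The fault is only that 11.3 gives the CI the assessment of all AEs.

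**Conclusion.** The point holds in two parts of unequal weight.

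First, the recording rule in 11.3 contradicts the safety outcome and the all-AE rules. If it is followed, the outcome is a CI-filtered subset and cannot be tabulated as 7.2.2 defines it. This rests on one assumption, that site staff take 11.3 as the operative recording rule; the documents do not say which section governs.

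Second, the REC exemption, the clocks and the choice of first assessor are compliance conflicts. They need settling but change nothing in the tabulation of the outcome.

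The size cannot be put as a number, because the count of excluded events depends on judgements not yet made. Two figures might tempt a reader. One is the zero-event limit, 1 − 0.025^(1/25) = 13.7% for 0 of 25. It supposes that no events are recorded, although every listed anticipated event is rated as high frequency, and it does not measure the contradiction. The other is the count of nine anticipated codes: snoring appears twice (04 and 06), so there are eight distinct entries.

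The change should be made before recruitment. It does not call the design into question.

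**What to change.** 1. Replace the restricting sentence in 11.3 so that every AE reported by a participant or noted by the team is recorded, with causality, seriousness and expectedness as separate fields. This brings it into line with 7.2.2, 11.2.3, 11.4.1 and 11.4.2, and device-related or clinically significant events can still be shown as subsets. No new route for asking participants is needed, since 11.3 already has them asked.
2. Reconcile 11.3 with 11.3.1 on who makes the initial assessment, keeping the PI, CI and Sponsor tiers of review.
3. Reconcile 11.2.3, 11.3, 11.3.2.1 and 11.4.3 so that each class of event has one Sponsor clock and one REC clock, each with a stated starting point. Which times apply is for the Sponsor to decide.
4. State in 11.3.2.1 whether the anticipated-event exemption covers serious related events, and make 11.3 and 11.4.3 agree with the answer.

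The cost is protocol wording and, probably, a few more AE records over about one night in 25 participants. Sample size, procedures and analysis of the device data are unaffected.
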